6.1.7 Handling of Dropouts and Missing Data

6.1.7.1 Missing Data

There will be no explicit imputation of missing data for effectiveness endpoints.

6.1.7.2 Seizure Diaries

Seizures are recorded in the Daily Seizure Diary, while the End of Day Diary provides Yes/No confirmation that that seizures were experienced for a specific date, or that the date was seizure free.

- If no seizures are entered in the DSD and the EDD confirms seizure freedom, the number of seizures for that date is zero.
- If seizures are entered in the DSD and the EDD states seizures freedom, the seizures recorded for that date supersede the EDD stating seizure freedom.
- If no seizures are entered in the DSD and there is no response in the EDD, that day will be considered to have missing diary data.
- If no seizures are entered in the DSD and there is a Yes response in the EDD, that day will be considered to have missing diary data.

Handling of missing date information for AEs:

- The term *missing date* refers to a completely missing date or to an incomplete date/partial date where parts are not available, e.g. missing month/day/year.
- Missing start and end date will be imputed conservatively, i.e. missing values will be imputed in such a way that the duration of the AE is considered with the longest possible duration and such that, whenever the AE may potentially start after first IMP, the AE will be handled as a TEAE.
- The missing start date and end date of AE will be imputed for the purpose of calculating treatment emergent status and assigning events to treatment periods using definitions given in the following table.

Table 8 Data Conventions for Missing Adverse Event Start or Stop Dates

Start or End Date Missing	Data Convention
Partial /Missing Start date	
Missing day – If Adverse event day is missing but month and year are present then Impute the 1st of the month unless month is same as month of first dose of study drug then impute first dose date.
 
Missing day and month – If adverse event day and month are both missing but year is present then impute 1st January unless year is the same as first dose date then impute first dose date.
 
Completely missing – impute first dose date unless the end date suggests it could have started prior to this in which case impute the 1st January of the same year as the end date.
 
When imputing a start date, ensure that the new imputed date is sensible i.e. is prior to the end date of the AE.

Partial /Missing End date	
If the AE is “ongoing”, do not impute an end date.
 
The following applies to a missing end date where the AE is not “ongoing”:
 
Missing day – If AE end day is missing but month and year are present then Impute the last day of the month unless month is same as month of last dose of study drug then impute last dose date.
 
Missing day and month – If AE has missing day and month but year is present then impute 31st December unless year is the same as the last dose date then impute last dose date.
 
Completely Missing – need to look at whether the AE is still ongoing before imputing a date and when it started in relation to study drug. If the ongoing flag is missing then assume that AE is still present (i.e. do not impute a date). If the AE has stopped and start date is prior to first dose date then impute the 1st dose date, if it started on or after first dose date then impute a date that is after the last dose date.

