6.3.1.1 Variables (Estimands)

Two key CSF-related variables will be defined:

- (1) the difference in convulsive seizure frequency per 28 days (CSF) for the open-label Treatment Period (Day1 to EOS) compared to the Baseline (Core Study);
- (2) the difference in CSF for the Month2 to EOS (Day 31 to EOS) time point compared to the Baseline (Core).

Additional variables associated with the assessment of CSF are:

- Baseline (Core), Core Study (T+M), Core Study Final Week [Note: The Core Study Final Week is a subset of the Core Study (T+M) period.]

- CSF during the following time intervals: Month 1, Month 2, Month 3, Month 4-6, Month 7-9, Month 10-12, Month 13-15, Month 15-18, Month 19-21, Month 22-24, Month 25-27, Month 28-30, Month 31-33 and Month 34-36.

The frequency of convulsive seizures during a given interval will be derived from the number and type of events recorded in subject diaries. For each subject, the seizure frequency per 28 days will be calculated as the number of seizures recorded during the period, divided by the number of days in the period and multiplied by 28. The convulsive seizure frequency will be calculated from all available data collected during the relevant interval.

The Baseline (Core) convulsive seizure frequency, or CSF_{BC} , is calculated as in the Core Study using the CSF from the 42 days immediately preceding the Randomization visit in the Core Study. For any individual subject, the convulsive seizure frequency per 28 days during the baseline period (CSF_{BC}) will be derived as follows:

$$CSF_{BC} = \frac{28 \times \text{Total number of convulsive seizures during the core study baseline period}}{\text{Total number of days in the core study baseline period with nonmissing diary data}}$$

For each treatment group, the mean is obtained by averaging over the subjects in the treatment group.

The convulsive seizure frequency per 28 days for the Core Study T+M period (CSF_{CTM}) is defined below:

$$CSF_{CTM} = \frac{28 \times \text{Total number of convulsive seizures during the core study T + M period}}{\text{Total number of days in the core study T + M period with nonmissing diary data}}$$

The convulsive seizure frequency per 28 days for the Core Study Final Week of T+M (CSF_{CSFW}) is defined below:

$$CSF_{CSFW} = \frac{28 \times \text{Total number of convulsive seizures during the core study final week}}{\text{Total number of days with nonmissing diary data during the core study final week}}$$

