Additionally for the other intervals (Month 1 through Month 36) defined in Table 7a, the convulsive seizure frequency per 28 days for that interval, $CSF_{OLE,i}$, $i=1, 2, 3, \dots, 14$, is defined as follows:

$$CSF_{OLE,i} = \frac{28 \times \text{Total number of convulsive seizures in the } i\text{th interval}}{\text{Total number of days in the } i\text{th interval with nonmissing diary data}}$$

The two key effectiveness measures, CSF_{E1} and CSF_{E2} , will be calculated as follows:

$$CSF_{E1} = \frac{28 \times \text{Total number of convulsive seizures from Day 1 to EOS}}{\text{Total number of days from Day 1 to EOS with nonmissing diary data}}$$

$$CSF_{E2} = \frac{28 \times \text{Total number of convulsive seizures from Day 31 to EOS}}{\text{Total number of days from Day 31 to EOS with nonmissing diary data}}$$

For each analysis group, the mean is obtained by averaging over the subjects in the analysis group.

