6.3.2.4 Duration of the Longest Interval between Seizures

The duration of the longest interval (in days) between convulsive seizures will be analyzed.

For each subject, the longest interval between convulsive seizures will be calculated over the entire OLE period. This will be derived as the maximum of the number of days between consecutive convulsive seizures. The intervals between consecutive convulsive seizures (gaps) will be calculated as below, after which the longest interval between convulsive seizures will be derived.

If a subject has two consecutive days of missing diary data, the current seizure-free interval will be ended on the first date of missing diary data, and a new one begun on the next date that diary data are available and no seizure occurs. [In that case, for purpose of calculation of this variable, all intervening days, after the 2nd day, with missing diary data, will be assumed to have a convulsive seizure occurrence, until the first available date with non-missing diary data.]

Let Date0 (=Day1) be the first day of treatment. If convulsive seizures occur on five days having dates as Date1, Date2, Date3, Date4 and Date5, where Date5 > Date4 > Date3 > Date2 > Date1 \geq Date0, and let LDT = Last date of treatment in the OLE treatment period, where LDT \geq Date5, then the time interval between convulsive seizures will be calculated as follows:

$$I1 = \text{Date2} - \text{Date1}$$

$$I2 = \text{Date3} - \text{Date2}$$

$$I3 = \text{Date4} - \text{Date3}$$

$$I4 = \text{Date5} - \text{Date4}$$

For completeness, we calculate the time to the first seizure as

$$I0 = \text{Date1} - \text{Date0}$$

and the time from the last seizure to end of treatment as

$$I5 = \text{LDT} - \text{Date5}$$

Here the duration of the longest interval = Maximum (I0, I1, I2, I3, I4, I5).

If the subject does not experience a seizure during treatment, then the last available diary date will be used to compute the duration of the longest interval as follows:

$$\text{The longest interval} = \text{last available diary date} - \text{Date0}$$

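### A day the caregiver confirmed as a seizure day, but without a seizure entry, is set to missing, so it can be reported as seizure freedom and bridged in the longest seizure-free interval

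*SAP*

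**What the plan says.** Section 6.1.7.2 uses two diary sources. Seizures are entered in the DSD, and "the End of Day Diary provides Yes/No confirmation that that seizures were experienced for a specific date", or that the date was free of seizures. Four combinations are listed:

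- No DSD entry, EDD seizure-free: zero seizures.
- DSD entry, EDD seizure-free: "the seizures recorded for that date supersede the EDD stating seizure freedom".
- No DSD entry, no EDD response: missing.
- No DSD entry, EDD Yes: "there is a Yes response in the EDD, that day will be considered to have missing diary data".

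Section 6.1.7.1 adds: "There will be no explicit imputation of missing data for effectiveness endpoints". The CSF formulas in Section 6.3.1.1 divide by days with diary data; for the first key endpoint the denominator is "Total number of days from Day 1 to EOS with nonmissing diary data".

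For the longest interval, Section 6.3.2.4 says: "If a subject has two consecutive days of missing diary data, the current seizure-free interval will be ended on the first date" of missing data. Missing days after the second in a run are then taken as convulsive seizure days. "If the subject does not experience a seizure during treatment, then the last available diary date will be used to compute" the interval, counted from the first treatment day.

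**The concern.** An EDD Yes is positive evidence that a seizure occurred, yet the plan gives it the same status as silence. In the reverse conflict the evidence of seizures prevails, so the two conflicts are resolved on different principles. Elsewhere the plan does not discard an occurrence because its count is unknown: the footnotes to Listings 16.2.6.1 and 16.2.6.2 set the number of seizures to 3 for clusters with no number recorded.

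Section 6.3.2.4 sharpens the problem. It assumes a convulsive seizure on days about which nothing may be known (missing days after the second in a run), but lets an isolated day that the caregiver confirmed as a seizure day pass inside a seizure-free interval.

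At stake are the results that a single seizure can overturn: the 100% reduction category (Section 6.3.2.3, Table 14.2.2.1) and the longest interval. No count of these days and no sensitivity analysis is planned.

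**Working it through.** The SAP gives no figure for this point, so there is none to reproduce. The SAP's formulas are applied here to constructed diaries.

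**Inputs.** CSF = 28 × seizures / non-missing days (6.3.1.1). Percentage change = (CSF − baseline) × 100 / baseline (6.3.1.2). Longest interval = maximum gap, including the time from Day 1 to the first seizure and from the last seizure to the end (6.3.2.4). The core baseline is taken "using the CSF from the 42 days immediately preceding the Randomization visit in the Core Study". Day 1085 is the Month 36 target day in Tables 4 and 5. The diaries are assumed, and where the day is kept, the EDD Yes is assumed to be convulsive.

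**1. Longest interval.** No recorded seizure, one isolated EDD-Yes day at Day 543, diary to Day 1085.
- SAP rule: one missing day does not end the interval; 1085 − 1 = 1084 days.
- Day ends the interval: max(543 − 1, 1085 − 543) = 542 days.

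**2. 100% reduction.** Baseline 6 seizures in 42 days: 28 × 6/42 = 4.0. In a 30-day month the only event is one EDD-Yes day.
- SAP rule: 28 × 0/29 = 0, a 100% reduction.
- Counted as 1: 28 × 1/30 = 0.93, a change of −76.7%.
- Counted as 3: 28 × 3/30 = 2.80, a change of −30.0%.

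**3. 50% responder status.** Same baseline; two recorded seizures and one EDD-Yes day in 30 days.
- SAP rule: 28 × 2/29 = 1.93, −51.7%, a responder.
- Counted as 1: 28 × 3/30 = 2.80, −30.0%, not a responder.

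**4. Repeated isolated days.** One EDD-Yes day every 28 days to Day 1085 gives 38 days.
- SAP rule: CSF 0, 100% reduction, longest interval 1084 days.
- Counted as 1: CSF = 28 × 38/1085 = 0.98, longest interval 28 days.

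**5. Mean CSF.** Let s be the share of days with seizures, f the share of those with EDD Yes only, and g the share of seizure-free days lost to a blank EDD. A day with a DSD entry meets neither missing-day rule and is taken as kept. Then

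observed/true CSF = (1 − f) / [s(1 − f) + (1 − s)(1 − g)].

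| s | f | g | ratio |
|---|---|---|---|
| 8/28 | 10% | 0 | 0.926 |
| 8/28 | 20% | 0 | 0.848 |
| 4/28 | 10% | 0 | 0.913 |
| 4/28 | 20% | 0 | 0.824 |
| any | f = g | f = g | 1 |
| 8/28 | 10% | 20% | 0.9/(0.257 + 0.571) = 1.09 |

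The ratio can fall on either side of 1. The SAP gives neither f nor g.

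**The case against.** The strongest reply is that the rule need not favour treatment. A reader might infer that every seizure endpoint is pushed towards benefit, by 7% to 18% for CSF at f of 10% to 20%. That needs g = 0. A seizure-free day with a blank EDD is also lost, which raises CSF; with f = g the effect vanishes, and with g larger it reverses. If the same rule and the same f apply at baseline, the percentage change largely cancels as well. This part of the reply stands.

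The EDD Yes is also not stated to mean a convulsive seizure, and Listing 16.2.6.2 has several non-convulsive types. A reader might infer that each such day disproves convulsive seizure freedom. The documents support only that it leaves it unconfirmed. This stands too, and is why the CSF change belongs in a sensitivity analysis.

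A reader might further infer that the no-seizure formula in 6.3.2.4 ignores long diary gaps, so that diary days 1–60 and 900–1000 would give 999 days. The text does not support that. The two-day rule is stated for any subject and places assumed convulsive seizures on days 63–899, so this subject does not reach that formula and gets about 100 days.

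Finally, safety is the primary objective (2.1), Section 6.1.1 urges caution with within-group changes, 100% reduction is not among the thresholds in 2.2, and diary review at visits may resolve some conflicts. These points lower the priority. They do not answer the isolated-day result, which follows from the stated rules.

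**Conclusion.** The point holds in limited form and should be fixed; it is not a fatal flaw. A confirmed seizure day without an entry is treated as no information, and when isolated it passes inside a seizure-free interval. A subject whose only events are such days is reported with CSF 0, 100% reduction and an unbroken interval; in the single-day example, 1084 days instead of 542. The interval result concerns isolated days only, since two consecutive missing days already end the interval.

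For mean CSF and seizure-free days, neither the size nor the direction of the net effect can be determined from the SAP. How many subjects are misreported is unknown for the same reason.

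**What to change.** - **6.1.7.2:** flag a day with EDD Yes and no DSD entry as 'seizure day, type and count unknown' instead of missing.
- **6.3.2.4:** let such a day end the current seizure-free interval. The no-seizure formula needs no change.
- **6.3.2.2 (convulsive plus non-convulsive frequency):** count the day as at least 1 seizure, stated as an exception to 6.1.7.1.
- **CSF and all responder categories, including 100% reduction:** keep the present derivation. Add a sensitivity analysis that counts the day as 1 convulsive seizure, and as 3 as for clusters of unknown number. Apply it identically at baseline and in the OLE, and derive CSF and responder status from the same counts. Barring a subject from the 100% category while the same analysis reports CSF 0 would be inconsistent.
- **Reporting:** give the number of such days, and of blank-EDD days, at baseline and by OLE period.

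The cost is SAP wording, one derivation flag and one added analysis on diary data already collected. For the sensitivity analysis the baseline must be re-derived, so it will depart from the core-study values used in 6.3.1.1. Seizure-freedom results may look slightly less favourable, and some days with only non-convulsive seizures will be treated conservatively.

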Pre-OLE Phase	Baseline (OLE) Period – de novo subjects	This description here applies to the de novo subjects. This start date of this period be the date of screening. The end date of the period will be the last date prior to the first dose of study drug in Study ZX008-1503.
OLE Phase	OLE Treatment Period	The OLE Treatment Period consists of the 36-month period from Visit 1 of the OLE study through Visit 16 of the OLE study The OLE Treatment Period start date is the date of first dose in Study ZX008-1503. The OLE Treatment Period end date is the date of end of study visit, Visit 16/ET. For subjects who discontinue early from the study, the OLE Treatment Period end date will be the date of the ET visit - safety measures collected at the last clinic visit will be used even in the event that study drug was discontinued prior to the date of the visit. Note: Adverse events occurring up to Visit 17 are regarded as occurring during treatment. In addition, AEs occurring up to 30 days after the last dose date will be regarding as treatment emergent.
OLE Phase	Taper Period	The Taper period consists of 2 weeks starting from end of study/early termination visit (Visit 16) + 1 day. The end date of this period is the date recorded for Visit 17.
Post-OLE Phase	Post-OLE Period	The start date of the post-OLE period is the date of Visit 17, + 1 day for subjects who complete the OLE Treatment period, or the day after the date of end of taper, for subjects who discontinue early. [There is not explicit end date for the post-OLE Phase. However, if needed, this may be set to be 45 days after the date of Visit 19, or V17 date + 210.]

For the purpose of statistical analysis, visit windows around the target visit dates will be implemented to capture effectiveness and/or safety data within similar periods. These windows are distinct from the

permissible visit scheduling windows specified in the Visit Schedule in the protocol that are used for the conduct of the study.

The following rules will be used to window data into treatment periods for tabulations that are generated by time during the OLE Treatment period.

Table 7a. Time Intervals for Analysis Visits for Seizure Analysis*

Analysis Phase/Period	Scheduled Visit Number in ZX008-1503	Analysis Visit**	Time Interval (label on output)	Time Interval (Day)
Pre-OLE	N/A	-99	Baseline (Core)*	Core Study Day -42 to Day-1 of Core Study
Pre-OLE	N/A	-9	Core Study (T+M)*	Day 1 of Core Study to End of T+M in Core Study

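### Table 8 ends a partially dated AE at the last dose, which contradicts the SAP's longest-duration rule and can place the end before a known onset (minor)

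*SAP*

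**What the plan says.** The rules for missing AE dates stand in SAP Section 6.1.7.2, below the seizure-diary rules, and in Table 8.

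- **Principle.** The text says that "missing values will be imputed in such a way that the duration of the AE is considered with the longest possible duration". It also asks that an AE be handled as a TEAE whenever it could have started after first dosing.
- **End day missing (not ongoing).** "Impute the last day of the month unless month is same as month of last dose of study drug then impute last dose date".
- **End day and month missing.** "impute 31st December unless year is the same as the last dose date then impute last dose date".
- **End date completely missing, AE stopped.** "if it started on or after first dose date then impute a date that is after the last dose date".
- **Plausibility check.** "When imputing a start date, ensure that the new imputed date is sensible i.e. is prior to the end date of the AE". There is no equivalent for an imputed end date.

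Two other places show that AEs after the last dose are expected. Section 6.4.1 keeps AE observation open until the later of 15 days after the last dose and the last visit. Table 6 treats "AEs occurring up to 30 days after the last dose date" as treatment emergent.

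**The concern.** The two last-dose exceptions pull the end date forward exactly where the stated principle would push it back. They also disagree with the completely missing row of the same table, which places the end after the last dose. A stopped AE with no end date at all therefore gets a later end than one whose end month or year is known.

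For an AE that starts after the last dose, the imputed end can fall before a fully known onset, and nothing in Table 8 prevents it. What is at stake is AE duration, which two open-label shells report: Table 14.3.1.2.1.2 for resolved decreased appetite and hypophagia, and Table 14.3.1.10.2 for events in at least 5% of subjects.

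**Working it through.** The SAP states no figure on this point, so the check applies Table 8 to example records. The calendar dates are illustrative assumptions. Elapsed time is end minus start; counting both days inclusively adds 1 to every elapsed time below.

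**1. AE starting after the last dose, end day missing.** Last dose 10 March, onset 20 March, end recorded as March of the same year, not ongoing.
- The onset is 10 days after the last dose, inside both the 15-day observation period and the 30-day treatment-emergent period.
- Table 8: the end month is the last-dose month, so the end is 10 March, and 10 - 20 = -10 days.
- Longest possible: 31 March, and 31 - 20 = +11 days.

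**2. AE starting before the last dose.** Last dose 5 March 2019, onset 1 March 2019.
- End recorded as March 2019: Table 8 gives 5 March, so 5 - 1 = 4 days. The longest possible end, 31 March, gives 31 - 1 = 30 days. The shortfall is 26 days.
- End recorded as 2019 only: Table 8 again gives 5 March, 4 days. 31 December gives 305 days. The shortfall of 301 days is a calendar bound, not an expected effect.

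**3. General size.** Shortfall = latest date compatible with the partial record, minus last dose date, over every last-dose day of a 365-day year.
- Day missing: 0 to 30 days, mean 14.7 if the last-dose day is uniform over the year.
- Day and month missing: 0 to 364 days, mean 182, before any cap for real follow-up.
- If AE follow-up ends 15 days after the last dose, a cap there limits either shortfall to 15 days. If the last visit is later, the limit is correspondingly longer.

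The shortfall is zero only if the last dose falls on the last day of the month or year.

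**4. When the end precedes onset.** This needs all of the following: onset after the last dose, the AE not ongoing, the end date partial, and that partial end in the last-dose month (day missing) or last-dose year (day and month missing). If onset is uniform over days 1 to 15 after the last dose, about 74% of onsets fall in the last-dose month and 98% in the last-dose year; over days 1 to 30 the shares are 49% and 96%. These shares cover only the onset condition. They do not say how many AEs have a partial end date, which the SAP cannot tell us.

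**5. Completely missing start date.** Table 8 says to "impute first dose date unless the end date suggests it could have started prior to this", and in the excepted case to use 1 January of the end-date year. Take first dose 15 March and a known end of 20 April. Nearly any end date is compatible with an earlier start, so read literally the row gives 1 January, before first dose. The notes to the TEAE shells (for example Tables 14.3.1.1, 14.3.1.2.1 and 14.3.1.6) class a missing start date as treatment emergent unless the recorded parts of that date show otherwise. A wholly missing date has no recorded parts, so the AE is a TEAE there. The row and the notes point in different directions.

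**The case against.** **The imputation may not feed durations.** Section 6.1.7.2 ties it to treatment-emergent status and period assignment, and no shell note says that imputed end dates enter the duration summaries. This stands in part: the use is implied, not stated. But the same section names duration as a governing aim, the two open-label shells report it, and no other rule for partial end dates is given.

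**The reach is narrow.** This stands. Table 14.3.1.10.1 is outside it, because its durations are limited to the double-blind study. Table 14.3.1.10.2 takes only events in at least 5% of subjects and, for repeated events, the earliest occurrence. Table 14.3.1.2.1.2 covers two terms. An AE ending in a later month than the last dose, with its month known, gets that month's last day as intended.

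**A reader might infer that TEAEs are lost.** The start-date example in the working could suggest that possible TEAEs drop out of the main safety tables. The documents do not support that. The shell notes keep such an AE as treatment emergent, and so does the principle in Section 6.1.7.2. The natural reading of the row is an end date before first dose, so this is loose wording in conflict with the notes. The end-date rows do not affect TEAE status either, because that rests on the start date.

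**A reader might take the year-only shortfall as the real effect.** It is a calendar bound. The AE must be recorded as not ongoing, AE observation is limited, and the cardiac follow-up visits collect only cardiac-safety AEs (footnotes to Tables 4 and 5). A sensible cap removes most of it.

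**Conclusion.** The last-dose exceptions in Table 8 are wrong as written. They contradict the longest-duration principle in the same section and the completely missing row of the same table. For an AE that starts after the last dose they can produce an impossible end date: -10 days against up to +11 in the example. These conclusions follow from the text alone; only the calendar dates are assumed.

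The consequence is minor. It reaches durations in Tables 14.3.1.2.1.2 and 14.3.1.10.2 if imputed end dates are used there, and only for non-ongoing AEs with a partial end date in the last-dose month or year. How many there are is unknown. TEAE incidence, the main safety output, is unchanged.

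**What to change.** In Table 8:

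1. Delete the two last-dose exceptions in the end-date rows. Impute the last day of the month, or 31 December when only the year is known, capped at the end of AE follow-up or last contact and never before the AE start.
2. Extend the plausibility check to imputed end dates.
3. For a completely missing start date, impute the first dose date unless the known or partial end date is before first dose. This matches the shell notes.

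It would also help to state whether imputed end dates are used in Tables 14.3.1.2.1.2 and 14.3.1.10.2.

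The cost is a few lines of Table 8 and a minor change to the date-imputation code. No further data are needed.
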